### Amendment for telehealth option

Video/telehealth Standard Practices

VA Video Connect (VVC) will be the preferred platform that will be used for video interactions with research participants. In the event that VVC fails, we will follow current VA guidance and use currently approved patient-facing platforms.

We will use standard video/telehealth practices including verifying the participant's identity, inquiring whether they have privacy during the visit, as well as obtaining their location and an emergency contact, in case of an emergency during the visit.

Our overall procedure for monitoring and reporting study-related adverse events includes:

Step 1: If a participant reports or monitoring reveals a study-related adverse event, research staff will report this to the Principal Investigator ([name]). When [name] is unavailable, [name] (study co-investigator) will be contacted. The research staff will closely adhere to VAGLA emergency reporting policies and procedures.

- Step 2: If indicated, [name] will speak with the participant to determine the severity and likely cause of the concern. If medical examination is needed and the situation is non-emergent, the participant will be advised to go to the VA outpatient clinic.
- Step 3: [name] will report the event to the IRB and will make a determination whether study protocols should be modified for that participant, whether the participant should be withdrawn from the study, or whether the study protocols should be modified overall.
- Step 4: All concerns reported by research staff will be documented, whether they appear to be study-related, and will be reviewed monthly by [name].
- If a participant reports a high level of mental distress, or discloses suicidal ideation during the interview process, research staff will follow these steps:
- Step 1: Research staff will immediately contact [name] (or another immediately available clinician) who will do an assessment. If relevant, the participant will be provided with the telephone number for the VHA suicide prevention hotline or other local suicide prevention resources.
- Step 2: If needed, the participant will be taken by research staff to the mental health or primary care outpatient clinic for evaluation and/or treatment. For all life-threatening emergencies at our facility, we call 911 and notify VA police.
- Step 3: As above, events will be reported to the IRB and a determination will be made about the protocol and the appropriateness of the participant continuing in the study.

# Primary Analysis Plan

We plan to randomize 132 individuals, of whom we expect 13% to drop out (i.e., fail to complete assessments) by 6-months, yielding N=114 participants with complete data ( $\sim$  57 per group). We base this drop-out on our completed study ([name] VA Merit 08-295). We will include terms for stratification characteristics and covariates for baseline pain intensity, PHQ-9, and opioid use in all of the models. All analyses below assume  $\alpha$ =0.05, power=0.80, two-sided hypothesis tests, and intention-to-treat approach. Effect sizes are in the measure's natural units and Cohen's d (large=.8; medium=.5; small=.2).

- (H1a) Participants who receive MTcap will have increased likelihood of hypnotic discontinuation post-treatment and at 6 months follow-up compared with those who receive SGT+CBTI: Hypnotic discontinuation (yes=1/no=0) will be regressed on treatment group assignment (MTcap vs. SGT+CBTI) in two logistic regression models (post-treatment and 6 months follow-up). Sample size calculations establish that 114 participants will be adequate to detect a difference of 21% to 26% between the MTcap and SGT+CBTI groups, depending upon the discontinuation percentage of the SGT+CBTI group (59% to 63% at follow-up in prior studies). In our feasibility study, 100% discontinued hypnotics post-treatment. We will use multiple imputation.
- (H1b) Participants who receive MTcap will use less hypnotic medication post-treatment and at 6 months follow-up compared with those who receive SGT+CBTI: Two outcomes will be assessed: frequency (i.e., 0 to 7 days used) and quantity (i.e., average daily dose in diazepam milligram equivalents). For each outcome, we will fit a 2 (group) by 3 (time) general linear mixed model. Interaction terms will be used to assess the change in the outcome (baseline→post-treatment, baseline→6 months) for MTcap vs. SGT+CBTI. Power Analysis: We use statistics from our recent study, which found a baseline to 6-month correlation of *r*=0.83 (95% Cl=0.77-0.88) and a standard deviation (SD) of 1.94 for a similar outcome measure—"days used of medications commonly used for insomnia" (0 to 7 days used). Assuming r=0.83 and n=57 per group, we could detect a treatment effect of 0.60 (Cohen's *d*=0.30) (i.e. a difference of 6/10ths of a day between the groups). Assuming *r*=0.77 (i.e., using the LCL), we could detect a treatment effect of 0.70 days (Cohen's *d*=0.36). If we disregard data from our recent study, power calculations still show that we could detect a treatment effect of 1.02 days (Cohen's *d*=.53; i.e., detect a difference of 1 day between groups). For quantity of use, power calculations indicate that we could detect a treatment effect of *d*=.53 (medium effect).
- (H2) Participants who receive MTcap will have lower Insomnia Severity Index scores at 6 months follow-up compared to SGT+CBTI: We will fit a general linear mixed model, and an interaction term will assess the change in ISI from baseline to 6 months for MTcap vs. SGT+CBTI. Power Analysis: Our prior research shows an ISI SD=5.3 and *r*=0.39 (95% CI=0.24-0.52) between baseline ISI and 6 month follow-up ISI. Assuming this correlation and a sample size of N=57 per group, the study could detect an effect as small as 3.1 units on the ISI (or a Cohen's *d*=.58). Assuming *r*=0.24 (i.e., using the LCL), we could detect an effect as small as 3.43 units on the ISI (or a Cohen's *d*=.65). An effect of 4.0 units on the ISI has been

- determined to be clinically-meaningful in prior research, 103 which means that the proposed study would be able to detect effects that are clinically-meaningful (as well as effects that smaller than clinically-meaningful); both of these power analyses suggest that the study could detect effects that are between medium and large effects.
- (H3) Dysfunctional Beliefs and Attitudes About Sleep (DBAS) Medication Scale ratings will improve compared to SGT+CBTI post-treatment and at 6 months follow-up: We will fit a 2 (group) by 3 (time) general linear mixed model. Interaction terms will be used to assess the change in DBAS medication items (baseline→post-treatment, baseline→6 months) for MTcap vs. SGT+CBTI group. Power Analysis: Our prior research shows a DBAS-16 SD= 2.1 and *r*=0.55 (95% CI=0.39,0.64) between baseline DBAS and 6-month follow-up DBAS. Assuming this correlation and a sample size of N=57 per group, the study could detect an effect size of *d*=0.50, which is a difference of 1.1 units on the DBAS-16. Assuming *r*=0.39 (the LCL), we could detect an effect size of *d*=.58, corresponding to a 1.2 unit change.

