#### Randomization

Individuals who complete the baseline assessment and meet all inclusion/exclusion criteria will be randomly assigned to one of the two intervention groups: MTcap (N=66) or SGT+CBTI (N=66). Both interventions are described below. Randomization procedures will follow the CONSORT criteria for randomized trials. Stratified

randomization will be used to ensure that both groups are balanced in baseline hypnotic drug type half-life (i.e., temazepam/zolpidem; alprazolam/lorazepam; clonazepam) and gender. The study statistician will generate the stratified randomization sequence. A set of envelopes containing the group assignment will be generated and stored in a secure file drawer accessible only authorized staff. Once final eligibility is determined, the data manager will open the next envelope in sequence within the appropriate stratum.

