# Secondary Analysis Plan (H4)

[figure not shown]
We will test whether MTcap improves cognition (DSS, Symbol Copy; Trails A & B) and balance (One-leg balance) at post-treatment and 6-month follow-up, using general linear mixed model (see Hypothesis 3 above). Effect size calculations: For the most pessimistic case—no correlation between these measures at the two time points—a post-test only analysis could detect a difference of *d*=0.52.

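### If the promised stratification and covariate terms enter the mixed models as main effects, they have almost no influence on the change-from-baseline tests for H1b, H2, H3 and H4; the plan should say how they enter.

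*Combined protocol and SAP*

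**What the plan says.** All references are to the Combined protocol and SAP. The opening paragraph of the Primary Analysis Plan makes a general promise: "We will include terms for stratification characteristics and covariates for baseline pain intensity, PHQ-9, and opioid use in all of the models". The Randomization section names the stratification factors; groups are to be "balanced in baseline hypnotic drug type half-life (i.e., temazepam/zolpidem; alprazolam/lorazepam; clonazepam) and gender". That is three drug classes and gender.

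The continuous outcomes are then tested as changes from baseline:
- H1b is a two-group, three-time mixed model: "Interaction terms will be used to assess the change in the outcome".
- H2: "an interaction term will assess the change in ISI from baseline to 6 months".
- H3 has the same layout as H1b: "Interaction terms will be used to assess the change in DBAS medication items".
- H4, in the Secondary Analysis Plan, follows H3: "using general linear mixed model (see Hypothesis 3 above").

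Baseline is therefore one of the outcome visits in these models. The plan does not say whether the covariate terms are main effects only or also interact with time, and it does not enter the baseline outcome as a covariate. H1a is different: two logistic regressions, one per follow-up time, with no baseline outcome row.

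**The concern.** A characteristic that is fixed per person and enters as a main effect shifts all of that person's visits by the same amount. The group-by-time contrast is a difference in change from baseline, so the shift is subtracted out. The sponsor chose three covariates and stratified on two factors, presumably because it regards them as prognostic. An analyst who codes the sentence in the usual way would fit models that list all five terms and produce practically the same H1b, H2, H3 and H4 results as models with none.

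Two things are at stake. First, chance imbalance in a covariate that predicts change would go uncorrected in results reported as adjusted. Second, the stratification factors would not inform the standard error of the contrast.

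**Working it through.** **Inputs from the plan.** "0.05, power=0.80, two-sided hypothesis tests, and intention-to-treat approach" gives the test settings. "we expect 13% to drop out (i.e., fail to complete assessments) by 6-months, yielding N=114 participants with complete data" gives 57 per group. For H2 the SD is 5.3 and the baseline to 6-month correlation is r = 0.39. The strength of the covariates is not given anywhere, so every figure that depends on it is an assumption.

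**1. The plan's own figure.** For an unadjusted comparison of change, d = (1.960 + 0.842) × √(2/57) × √(2(1 − r)). For H2 this is 0.525 × √1.22 = 0.580, and 0.580 × 5.3 = 3.07 ISI units (3.10 with the t distribution). The plan states 0.58 and 3.1. The same formula gives 0.306 for H1b (stated 0.30) and 0.498 for H3 (stated 0.50). These stated effects therefore take no credit for covariates.

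**2. Why main effects cancel.** Write the outcome at visit t as μ(t) + a·group + b(t)·group + c·x + error, with b = 0 at baseline and x fixed per person. The change to 6 months is [μ(6) − μ(0)] + b(6)·group + [error(6) − error(0)]. The term c·x has gone. With complete data the estimate of b(6) is the difference in mean change, whatever x is.

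**3. Numerical check.** There were 200 simulated trials per row, with N = 132, three visits, SD 5.3, correlation 0.39 and unstructured covariance. Three covariates were fitted, one of them predictive. Shift is the absolute change in the 6-month estimate, in ISI units, when main effects are added.

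| Dropout; covariate effect at the three visits (SD, assumed) | Mean shift (max) | SE, no covariates | SE, main effects | SE, with time interaction |
|---|---|---|---|---|
| None; 0.4, 0.4, 0.4 | 0.000 (0.000) | 1.009 | 1.009 | 1.010 |
| None; 0.1, 0.5, 0.5 | 0.000 (0.000) | 1.009 | 1.009 | 0.941 |
| 13%; 0.4, 0.4, 0.4 | 0.07 (0.23) | 1.051 | 1.048 | 1.046 |
| 13%; 0.1, 0.5, 0.5 | 0.08 (0.39) | 1.049 | 1.041 | 0.979 |
| 13%, dependent on covariate and arm; 0.4, 0.4, 0.4 | 0.11 (0.42) | 1.059 | 1.054 | 1.056 |
| 13%, dependent on covariate and arm; 0.1, 0.5, 0.5 | 0.13 (0.37) | 1.048 | 1.042 | 0.982 |

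Cancellation is exact with complete data. With 13% dropout, main effects reduce the SE by 0.3% to 0.8%.

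**4. What an imbalance could do.** The SD of change is 5.3 × √1.22 = 5.85. Suppose one covariate is out of balance by 0.3 SD and explains 9% of the variance of change (both assumed). The shift is 0.3 × √0.09 × 5.85 = 0.53 ISI units, about half a standard error. In 300 simulated null trials with this imbalance and 13% dropout, the mean estimate was 0.52 without covariates, 0.52 with main effects and −0.02 with time interactions. With 66 per arm the SE of an imbalance is √(2/66) = 0.174 SD, so one of at least 0.3 SD arises in about 8.5% of trials for a given unstratified covariate.

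**5. What the interactions cost and gain.** Two drug-class contrasts, gender, pain, PHQ-9 and opioid use make k = 6 parameters per follow-up visit. With N = 114 the SE ratio is about √[(1 − R²) × (N − 3)/(N − k − 3)] = √[(1 − R²) × 111/105], where R² is the assumed share of change variance explained.

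| R² | SE ratio, formula | SE ratio, simulated | H2 detectable effect (3.1 × formula ratio) |
|---|---|---|---|
| 0 | 1.028 | about 1.03 | 3.19 |
| 5% | 1.002 | about 1.00 | 3.11 |
| 9% | 0.981 | 0.97 to 0.98 | 3.04 |
| 20% | 0.920 | 0.92 to 0.93 | 2.85 |

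**The case against.** The strongest reply is that the plan promises terms and does not say main effects only. Covariate-by-time terms are left open. That stands: the text does not show that the adjustment drops out of every test, although a reader might infer it. What the text does show is that its plain reading leaves the adjustment close to inert, and nothing in the plan rules that reading out.

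Second, subtracting baseline also removes imbalance in whatever a covariate adds equally to all visits. Only a covariate that predicts change leaves imbalance behind, and the documents give no evidence on which ones do. This also stands. In addition, drug class and gender are stratified, so the exposure is mainly through pain, PHQ-9 and opioid use. The 0.53-unit figure is conditional on two assumptions and is not an expected bias. The unadjusted contrast is unbiased over randomisations.

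Third, cancellation is not complete when data are missing. When dropout depended on covariate and arm, main effects moved the mean estimate by about 0.1 ISI unit in the right direction. For H4 balance, the baseline procedures for video and telephone visits omit the one-leg test, so incomplete pairs may be more common and the terms may act somewhat more there. To say that the terms do nothing would therefore be too strong.

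Fourth, a reader might infer that power is overstated. It is not, because the stated effects for H1b, H2 and H3 reproduce without covariates.

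**Conclusion.** The point holds in a limited form. Under the plain reading, the promised adjustment has no influence on the H1b, H2, H3 and H4 contrasts with complete data. With 13% dropout its influence is very small: an SE gain under 1% and a shift of about 0.1 ISI unit on average for an ISI-like outcome, against an SE of about 1.05. H4 balance may be a partial exception. The consequence is that results would be described as adjusted when they effectively are not, and that imbalance in a covariate predicting change would stay in the estimate. It does not make the tests invalid, change any stated detectable effect or touch H1a.

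This rests on main-effect entry and on reading the word baseline as covering PHQ-9 and opioid use as well as pain. The simulated covariate strengths and the R² values are assumptions. The precision argument alone would not justify the change, since the gain is about nil at 5% of change variance explained. The reason to act is that the written commitment should do what it says.

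**What to change.** Add one sentence to the opening paragraph of the Primary Analysis Plan: in the mixed models, each stratification factor and each covariate enters with its main effect and its interaction with time, and the group-by-time contrasts remain the tests. The logistic models need no change.

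An acceptable alternative is to model only the follow-up visits, with the baseline outcome as a covariate. Main-effect terms then do act. With the plan's r = 0.39, and before any credit for the other covariates, H2's detectable effect would be 0.525 × √(1 − 0.39²) = 0.483 SD, or 2.56 ISI units, against 3.07. For balance, this route needs a stated way of handling participants with no baseline test.

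Neither option needs new data. The interaction route spends six parameters per follow-up visit: about 3% in SE if the terms do not predict change, break-even near 5% of change variance explained, and a gain of about 2% to 3% at 9% and 7% to 8% at 20%, which would take H2's 3.1 units to roughly 2.9. The choice should be fixed before outcome data are examined by arm.

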Another mechanism that may be a viable target for achieving hypnotic discontinuation and sustaining long-term non-use is the placebo effect,  which is characterized by real improvements in sleep arising from psychosocial aspects of treatment rather than drug effects alone. We recently developed and tested the feasibility of an intervention that targets the placebo effect. Our intervention retains core components tested in prior studies for achieving hypnotic discontinuation (i.e., SGT+CBTI), but adds a novel feature—"masked" tapering. Masking is achieved by encapsulating hypnotics (prepared by a compounding pharmacy) so the patient, who has consented to a gradual taper, is unaware of the actual dose in each capsule until the end of the taper, when the tapering schedule is revealed to the patient. Towards the end of the taper, placebo capsules are used. Through novel cognitive exercises, the therapist uses masking as a tool to challenge expectancies about hypnotics, which may be contributing to chronic use, and to augment CBT-HW (e.g., preparing for withdrawal). Coupled with CBTI (i.e., stimulus control, sleep restriction, cognitive therapy for insomnia, and relaxation), the intervention targets the placebo effect and the factors contributing to insomnia symptoms and helps patients safely taper off their hypnotic and develop relapse prevention skills.

The objective of the proposed study is to test whether hypnotic discontinuation rates can be increased with a novel set of cognitive exercises that use supervised masked tapering as a core tool to challenge expectancies about hypnotics. In a 4-year randomized trial (N=132 participants), we will measure the effects of a 2-month program entitled, **M**asked **T**aper plus **c**ognitive behavioral therapy-**a**ugmented **p**rogram (MTcap), which combines novel cognitive behavioral therapy exercises, supervised masked hypnotic tapering, CBT-HW, and CBTI. We will compare outcomes in MTcap to a supervised unmasked (traditional) SGT+CBTI program post-treatment and at 6 months follow-up to determine whether the addition of the novel cognitive exercises and masked tapering reduces expectancies for hypnotics, improves hypnotic discontinuation rates, and improves insomnia symptoms. The rationale is that hypnotic-related placebo effects can be specifically targeted with our novel intervention. The following are the **primary aims** for the proposed project:

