Aim 1: Determine whether MTcap improves hypnotic discontinuation more than SGT+CBTI post-treatment and at 6 months follow-up.

- H1a: Participants who receive MTcap will have increased likelihood of hypnotic discontinuation posttreatment and at 6 months follow-up compared with those who receive SGT+CBTI.
- H1b: Participants who receive MTcap will use less hypnotic medication post-treatment and at 6 months follow-up compared with those who receive SGT+CBTI.
- Aim 2: Determine whether MTcap improves insomnia severity more than SGT+CBTI at 6 months follow-up.
- H2: Participants who receive MTcap will have lower Insomnia Severity Index scores at 6 months follow-up compared to SGT+CBTI.
- Aim 3: Determine whether MTcap improves expectancies about hypnotics more than SGT+CBTI post-treatment and at 6 months follow-up.
- H3: Dysfunctional Beliefs and Attitudes About Sleep (DBAS) Medication Scale ratings will improve compared to SGT+CBTI post-treatment and at 6 months follow-up.

A secondary aim is to compare balance and cognition in the MTcap arm compared with the SGT+CBTI arm at follow-up. We hypothesize that participants who receive MTcap will have better balance and cognition compared to those who receive SGT+CBTI post-treatment and at 6 months follow-up.

This proposed study will test the effects of an innovative intervention on chronic hypnotic use among older Veterans, which is a prevalent, high-priority, and challenging problem. The intervention was designed based on extensive feasibility testing. If successful, this novel intervention could lead be disseminated throughout the VA and lead to significant improvement in ongoing efforts to decrease chronic hypnotic use among older Veterans.

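### Nine contrasts under the primary aims are each tested at 0.05 with no lead test, and H1a has no rule for whether one or both time points must succeed

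*Combined protocol and SAP*

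**What the plan says.** Specific Aims presents Aims 1, 2 and 3 together as the "primary aims for the proposed project". H1a predicts "increased likelihood of hypnotic discontinuation posttreatment and at 6 months follow-up".

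The Primary Analysis Plan applies one set of operating characteristics to every analysis that follows: alpha 0.05, power 0.80, "two-sided hypothesis tests, and intention-to-treat approach". It then specifies:

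- H1a: discontinuation regressed on group "in two logistic regression models (post-treatment and 6 months follow-up"), so two tests.
- H1b: "Two outcomes will be assessed: frequency (i.e., 0 to 7 days used) and quantity", each with a change contrast to post-treatment and to 6 months, so four tests.
- H2: "an interaction term will assess the change in ISI from baseline to 6 months for MTcap vs. SGT+CBTI", so one test.
- H3: "Interaction terms will be used to assess the change in DBAS medication items" to post-treatment and to 6 months, so two tests.

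That makes nine. No section names a primary endpoint and time point, a testing order, a gatekeeping rule or a multiplicity adjustment. Nor does the plan say whether H1a succeeds on one time point or needs both.

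**The concern.** A plan that calls three aims primary, tests nine contrasts at 0.05 and does not say which result decides the trial leaves the success criterion to be chosen after the data are seen. The gap is sharpest for H1a, the discontinuation question that the study objective puts first. Its hypothesis joins the two time points with 'and', but the analysis fits them separately. A reader who sees no need to adjust across distinct aims still cannot tell from the plan what a positive H1a would be.

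The UCLA amendment under the Exploratory Analysis Plan adds a possible further choice. It repeats the analyses with extra data and does not say whether those results replace or accompany the originals.

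**Working it through.** **Inputs from the documents.** Two-sided alpha 0.05 and power 0.80 for each analysis; 132 randomised, 13% dropout, 114 analysed (57 per arm); H1a detectable difference 21 to 26 points with a comparator rate of 59% to 63%, given for follow-up only; 100% discontinuation post-treatment in the feasibility study.

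**Assumptions.** The correlation among the nine test statistics is not given, so a range is shown. Correlated results come from simulating 1,000,000 sets of equicorrelated normal test statistics.

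**1. The plan's own figures.** Dropout reproduces: 132 × 0.87 = 114.8. For H1a I used the unadjusted two-proportion formula

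power = Φ{[Δ√n − 1.96√(2p̄(1−p̄))] / √(p₁(1−p₁) + p₂(1−p₂))}.

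With n = 57, p₁ = 0.59 and Δ = 0.21: (1.586 − 1.276)/0.634 = 0.49, so power is 69%. With p₁ = 0.63 it is 73%. At 26 points, power is 88% and 91%. Solving for 80% power gives 23.6 points (comparator 59%) and 22.7 points (63%). Other two-sided methods (unpooled, arcsine, continuity-corrected, Fisher) span 22.2 to 25.2 points. None turns 59% to 63% into 21 to 26 points.

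**2. Any one of nine counts as success.** If independent, 1 − 0.95⁹ = 0.370.

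| Common correlation (assumed) | Any of 9 significant | H1a: either of 2 significant | H1a: both significant, each at 80% power |
|---|---|---|---|
| 0 | 37% | 9.8% | 64% |
| 0.3 | 33% | 9.5% | 67% |
| 0.5 | 27% | 9.1% | 69% |
| 0.7 | 20% | 8.3% | 71% |
| 0.9 | 12% | 7.0% | 75% |

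**3. Both time points required throughout.** H1b and H3 carry the same wording as H1a. Enforced everywhere, it leaves five hypotheses: four that need two significant tests, and H2 alone. Under the global null with independence, 1 − (1 − 0.05²)⁴ × 0.95 = 0.059. Common correlations of 0.3 to 0.9 give 6.5% to 7.3%. Two assumed structures with stronger correlation within outcome or within time point gave 8% and 10%. In the least favourable independent case, one test of each pair is certain to succeed and the other is null, so each pair has error 0.05 and the total is 1 − 0.95⁵ = 22.6%. If both time points are required for H1a only, the other seven contrasts still carry up to 1 − 0.95⁷ = 30%.

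**4. H1a power if both are needed.** Joint power cannot exceed that of the weaker test. The last column of the table assumes 80% at each time point. If post-treatment discontinuation were 95% on MTcap against an assumed 59% to 63%, that test would have 99.8% to 99.2% power, and joint power under independence would be 0.80 × 0.998 = 79.8% to 0.80 × 0.992 = 79.4%. The plan gives no post-treatment comparator rate, so its place in the range is unknown.

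**The case against.** The strongest reply is that the aims ask separate questions about use, insomnia severity and beliefs; that adjustment across separate aims is contested; and that no section says any one significant result makes the trial positive. The objective is framed around discontinuation, and H1a comes first. All of that stands. It shows what the lead endpoint probably is, but it supplies neither a time point nor a success rule.

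Three stronger readings are tempting and are not supported:

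- A reader might take 20% to 37% as the trial's error rate. The lower figure depends on an assumed correlation near 0.7, and 0.9 gives 12%. The whole range applies only under an any-one-counts rule. Requiring both time points throughout brings the global-null rate down to about 6% to 7% at a common correlation.
- A reader might infer that alpha 0.05 and power 0.80 cannot both be true for discontinuation. For a single 6-month test they can, and requiring both time points still respects 0.05.
- A reader might conclude that either the trial-wide error is inflated or H1a's power fails. These concern different sets of tests, nine and two, and are not alternatives.

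It is also fair that the feasibility result of 100% post-treatment could make the loss of joint power close to nil.

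**Conclusion.** The point holds in a limited form. Nine contrasts sit under the primary aims, each at two-sided 0.05, with no lead test or order, and H1a has no success rule. How far the error rate exceeds 5% depends on a rule that the plan does not state: up to 37% if any contrast counts, about 6% to 7% under the global null if both time points are enforced throughout (assuming a common correlation), and up to 22.6% in the least favourable independent case. For H1a alone, either-suffices gives about 7% to 10% type I error. Both-needed makes the 6-month test's power a ceiling.

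Separately, the stated 21-point end of the detectable range is too optimistic for 57 per arm. The analyses remain usable, but what counts as success should be fixed before results are seen.

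**What to change.** Name H1a at 6 months as the single primary test at two-sided 0.05. This fits the plan's own sizing: the comparator rates are given for follow-up and dropout is projected to 6 months. Make H1a post-treatment a key secondary test. Treat the other seven contrasts either as secondary, reported as estimates with confidence intervals, or in a pre-specified gatekeeping order. That order is for the sponsor to choose; the documents do not dictate one.

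State that the power claim applies to the 6-month H1a test only, and restate its detectable difference as about 23 to 24 points at 57 per arm, with 69% to 73% power at 21 points. Say also whether analyses with the UCLA data replace or supplement the originals.

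The cost is a paragraph in the plan. The lead test loses no power and no patients are added. The downside is that the other hypotheses lose an automatic confirmatory claim. By comparison, Bonferroni over nine tests would cut H1a power to about 50% at the recomputed detectable difference, or need 221 randomised to restore 80%. Requiring both H1a time points with 80% joint power, if independent and of equal power, needs √0.80 = 89.4% at each: 75 per arm analysed, or 150/0.87 = 173 randomised.

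### H1a's detectable difference of 21% to 26% does not follow from its stated inputs, which give about 23 to 24 points; power for 21 points is about 69% to 73%, not 80%

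*Combined protocol and SAP*

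**What the plan says.** The opening of the Primary Analysis Plan sets the common assumptions. On numbers it says "We plan to randomize 132 individuals, of whom we expect 13% to drop out". The result after that loss is given as "yielding N=114 participants with complete data", or about 57 per group. The error rates are two-sided 0.05 and "power=0.80, two-sided hypothesis tests, and intention-to-treat approach".

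Under (H1a), discontinuation is compared between arms by logistic regression, with one model post-treatment and one at 6 months. The power statement is that "114 participants will be adequate to detect a difference of 21% to 26% between the MTcap and SGT+CBTI groups". The plan explains the width of this range by the control arm's rate, which it takes from earlier trials: "depending upon the discontinuation percentage of the SGT+CBTI group (59% to 63% at follow-up". The paragraph also gives the feasibility result (all participants discontinued by the end of treatment) and says that multiple imputation will be used. It names no sample-size formula, continuity correction or covariate adjustment factor, and gives no control rate other than 59% to 63%.

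**The concern.** The sentence attributes the width of its range to the control rate, and gives that rate. Every input needed to check it is therefore on the page. Two features look wrong. A 4-point change in a control rate near 60% should barely move the detectable difference, yet the range is 5 points wide. And 21 points looks too small for 57 per arm at these rates.

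This sentence is the only support for the claim that 114 completers suffice for the first-listed primary hypothesis. A reader who accepts the lower end will believe that a true 21-point benefit has a 20% chance of being missed. If the real chance is higher, a null or borderline result would be over-interpreted as evidence against a benefit of that size.

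**Working it through.** **Inputs** (all from the Primary Analysis Plan, except allocation, which is in the Randomization section)

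- Complete cases: 132 × 0.87 = 114.8, stated as 114, so n = 57 per arm; allocation is 1:1 (66 and 66 randomized).
- Two-sided α = 0.05 (z = 1.960); power 0.80 (z = 0.8416).
- Control rate p0 = 0.59 to 0.63; H1a expects a higher rate p1 with MTcap.
- The comparison is unadjusted, because the plan gives no figure for what the covariates explain.

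**Formulas** (pooled normal approximation), with d = p1 − p0, p̄ = (p0 + p1)/2, V0 = 2p̄(1 − p̄) and V1 = p0(1 − p0) + p1(1 − p1):

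- n per arm = [1.960·√V0 + 0.8416·√V1]² / d²
- power = Φ{ [d·√n − 1.960·√V0] / √V1 }

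**Step 1: try to reproduce the plan's 21 and 26 points.** With √57 = 7.550:

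| p0 → p1 | √V0 | √V1 | n per arm for 80% power | Power at 57 per arm |
|---|---|---|---|---|
| 59% → 80% (21) | 0.6511 | 0.6340 | (1.2762 + 0.5336)²/0.0441 = 74.3, so 75 | Φ(0.488) = 68.7% |
| 63% → 84% (21) | 0.6241 | 0.6062 | (1.2233 + 0.5102)²/0.0441 = 68.1, so 69 | Φ(0.597) = 72.5% |
| 59% → 85% (26) | 0.6350 | 0.6078 | (1.2445 + 0.5115)²/0.0676 = 45.6, so 46 | Φ(1.182) = 88.1% |
| 63% → 89% (26) | 0.6040 | 0.5753 | (1.1838 + 0.4842)²/0.0676 = 41.2, so 42 | Φ(1.354) = 91.2% |

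Neither figure is reproduced. Exact enumeration of the chi-square test gives power of 69.9% and 73.5% for 21 points (from 59% and 63%), close to the approximation.

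**Step 2: solve for the difference that does have 80% power at 57 per arm.**

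| Method | From 59% | From 63% | Spread |
|---|---|---|---|
| Log-odds, null variance | 23.0 | 22.0 | 1.0 |
| Unpooled normal | 23.1 | 22.2 | 0.9 |
| Exact enumeration of chi-square | 23.4 | 22.5 | 0.9 |
| Arcsine | 23.4 | 22.4 | 1.0 |
| Pooled normal | 23.6 | 22.7 | 0.9 |
| Log-odds Wald | 24.4 | 23.6 | 0.8 |
| Fisher exact | 24.9 | 23.8 | 1.1 |
| Continuity-corrected | 25.1 | 24.2 | 0.9 |

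All values lie between 22.0 and 25.1. The spread across the cited control rates is about 1 point under every method.

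**Step 3: look for inputs that would give the plan's figures.** With the pooled formula at 57 per arm, 21 points needs a control rate near 69%. The detectable difference peaks at 26.0, at a control rate near 37%. With a continuity correction, 21 points falls near 73% and 26 points near 55%. With 66 per arm, the pooled formula gives 22.1 (59%) and 21.3 (63%). None of these inputs appears in the sentence, and no single change gives both ends at 59% to 63%.

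**The case against.** Four arguments can be made for the plan.

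*The upper end depends on the formula.* The continuity-corrected figure from 59% is 25.1, within a point of 26. The model includes stratification terms and covariates, and a variance inflation of about 25% with the pooled formula (57/45.6) would make 26 points from 59% exact. This stands in part: how cautious 26 is depends on the method. But the plan states no inflation, and one that large also lifts the 63% figure to about 25, further from 21.

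*The range may cover other control rates.* H1a has two time points, and the cited rates are labelled as follow-up rates. A higher post-treatment control rate is plausible, and with a continuity correction a span of roughly 55% to 73% would give 26 down to 21. This is possible. But the sentence ties the range to 59% to 63% and mentions no wider span, so the reader cannot recover it.

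*Intention-to-treat with imputation uses all 132.* At 66 per arm, power for 21 points from 63% is 78.7%. But imputation does not restore all the missing information, the sentence says 114, and the larger number moves the result further from 26. It remains true that the power figures here are complete-case and unadjusted.

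*The consequence is small.* The recalculated 23 to 24 lies inside 21 to 26. If MTcap reached even 90% discontinuation, 57 per arm would give about 98% power against 59% and 94% against 63%. This stands, and it is why the point calls for a correction to the text and not to the design.

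**Conclusion.** The concern holds. At 57 per arm, two-sided 0.05 and 80% power, control rates of 59% to 63% give a detectable difference of about 23 to 24 points, not 21 to 26. By the pooled formula the lower end is about 1.7 points too favourable (22.7 − 21) and the upper end about 2.4 points too cautious (26 − 23.6).

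The lower end is the one to correct: the chance of missing a true 21-point benefit is about 27% to 31%, against the 20% implied. That end fails under every two-sided method tried. The upper end errs in the safe direction, and its excess shrinks to under 1 point with a continuity correction.

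These figures assume an unadjusted comparison of 57 complete cases per arm and that 59% to 63% is the full set of control rates used. If the calculation used other rates or another method, the defect is an undisclosed input, and the sentence is still wrong as it reads.

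**What to change.** Replace the H1a power sentence with wording such as:

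> With 57 participants per arm, the study has 80% power at two-sided 0.05 to detect a difference in discontinuation of about 23 to 24 percentage points (from 59% to 83%, or from 63% to 86%; pooled normal approximation, unadjusted). Power for a 21-point difference is about 69% to 73%.

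If a continuity-corrected or Fisher calculation is preferred, name it and give about 24 to 25 points instead. If 21 and 26 came from other control rates, such as post-treatment rates, or from an allowance for covariates, state the rates, their source, the allowance and the formula.

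The cost is wording only. No participants are added, and the test and conduct do not change. The stated range becomes about 2 points less favourable at the lower end and about 2 points more favourable at the upper end.
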